PMA	Premarket Approval
PN Q	Pediatric Nutrition Questionnaire
SAE	Serious Adverse Event/Serious Adverse Experience
SCAS	Spence Child Anxiety Scale Questionnaire
SD	Standard Deviation
SIRS	Systemic Inflammatory Response Syndrome
SOP	Standard Operating Procedure
TBWL	Total Body Weight Loss
UADE	Unanticipated Adverse Device Effect
US	Ultrasound
WMC	Weight Management Clinic

Study Summary

Title	Safety and Efficacy of Endoscopically Placed Intragastric Balloon in Obese Adolescents with Comorbidities – A Pilot Study
Running Title	IGB in Obese Adolescents with Comorbidities
IRB Protocol Number	15-009191
Phase	Pilot
Methodology	Open Label
Overall Study Duration	60-64 Weeks
Subject Participation Duration	12 months
Objectives	
 • Determine if placement of IGB for a period of 6 months is safe and results in weight loss with metabolic improvement in obese adolescents • Determine if IGB is well tolerated by adolescents • Determine if weight loss is sustainable after the IGB removal through integrating the subjects in the pediatric weight management program
Number of Subjects	12
Diagnosis and Main Inclusion Criteria	Subjects must have $\text{BMI} > 35 \text{ kg/m}^2$ with one severe comorbidity or $\text{BMI} > 40 \text{ kg/m}^2$ with two or more mild comorbidities
Study Device	Orbera Intragastric Balloon (Apollo Endosurgery Austin, TX)
Duration of Exposure	6 months
Statistical Methodology	The study results will be largely descriptive. Standard statistical analysis will be performed. Multiple linear and logistic regression analysis will be performed to determine significant variables relating to risk. A p-value of < 0.05 will be considered statistically significant.

1 Introduction

This document is a protocol for a human research study. This study will be carried out in accordance with the procedures described in this protocol, applicable United States government regulations and Mayo Clinic policies and procedures.

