Another application comes from the growing evidence regarding the epidemiology of DM2 in adolescents and its multisystem health complications, but treatment options have lagged behind. Disease progression in adolescents occurs despite aggressive medical therapy and tends to be more aggressive than in adults with DM2. All of that evidence resulted in increased interest in the application of bariatric intervention for adolescents with DM2 and morbid obesity. This was the recommendation of recent review by Shah et al, who recommended bariatric intervention because of the evidence demonstrating improvement or remission in many adults with diabetes after bariatric intervention. [22]

The rates of adverse events after implantation of the Orbera balloon are pooled from a manual review of 68 studies (8500 implantations) and are summarized in Figure 1. Pain and nausea are frequent side-effects after Orbera balloon implantation, occurring in up to 33.7% of subjects. Medications such as proton pump inhibitors, antispasmodic drugs, and antiemetics are usually prescribed prophylactically before, during, and after balloon placement to prevent

or minimize these expected common side effects. Serious side-effects with Orbera balloon are rare with an incidence of migration and gastric perforation of 1.4% and 0.1%, respectively. Most of the reported perforations with the Orbera were in patients who had undergone previous gastric surgeries, which is a contraindication for use in the US.[18]

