3.4 Primary Safety Endpoints

- Incidence of all serious adverse events including unanticipated adverse effects (balloon migration, small bowel obstruction, luminal GI perforation, ulcer formation, liver abscess formation, bleeding, biliary obstruction or injury, aspiration, infection, abdominal pain requiring hospitalization, nausea and dehydration requiring intravenous fluids, and death). All adverse events will be captured and graded for severity using Common Terminology Criteria for Adverse Events (CTCAE) scale. [27]
- Early balloon intolerance requiring removal.
- Balloon deflation rates (see Orbera PMA)

4 Subject Selection, Enrollment and Withdrawal

Adolescents age 14-17 who are seen at Mayo Clinic-Rochester in community pediatrics, pediatric GI, pediatric endocrinology, or the pediatric weight management clinic, or at Mayo Clinic Health System (MCHS) with a $BMI > 35 \text{ kg/m}^2$ with one severe comorbidity or $BMI > 40 \text{ kg/m}^2$ with two or more mild comorbidities as per the ESPAGHAN guidelines for

bariatric intervention in children with severe obesity. [14] Recent meta-analysis supported the safety and benefit of IGB use in higher BMI (range 35-55).[24] Subjects that meet these criteria can be referred to the PI, co-investigators, or study coordinator to approach for possible participation in this research study.

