6.6 Management of Device Failure

If there is a device malfunction during the initial endoscopic placement (e.g. balloon is deflated, perforated, or other failure), then the balloon will be replaced with a new balloon during the same procedure.

During the follow-up visits or phone calls, if there is concern that the balloon is malfunctioning or may be deflated after successful placement, which can be suggested by the lack of satiety, ability to eat larger meals, or failure to lose weight during two consecutive follow-up visits, an abdominal ultrasound assessment will be performed.

- If the balloon is intact, then no endoscopic assessment will be indicated.
- If there is evidence of balloon malfunction without complication, a new balloon will be placed.
- If the balloon is deflated in the stomach, it will be replaced endoscopically with a new balloon.
- If the balloon is not in the stomach and subject has no symptoms of small bowel obstruction, the subject will be observed for 3 days for spontaneous passage of the balloon. Serial abdominal x-rays will be performed to monitor progression of the balloon in addition to clinical follow-up of signs and symptoms that may indicate a small bowel obstruction (e.g. pain, bilious vomiting, etc.) If the balloon doesn't pass, an attempt to remove it endoscopically will be performed. If not reachable by the endoscopy, the subject will be referred for surgical removal.

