This is a pilot study of 12 subjects only, so results will be largely descriptive. Standard statistical analysis will be performed. We will use t-tests or alternative measures will be used to test whether weight loss was significant from baseline to each of the follow up points.

8 Safety and Adverse Events

All adverse events occurring during the study, including those not meeting the criteria of an Unanticipated Adverse Device Effect (UADE) will be recorded on the appropriate case report form. Records of these events will be maintained and reports submitted to the FDA and IRB according to the regulatory requirements. All adverse events will be reported. Expected clinical adverse events and anticipated adverse device effects are those listed in Section 1.5.2.

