- Unanticipated: (i.e. unexpected) problems or events are those that are not already described as potential risks in the protocol, consent document, not listed in the Investigator's Brochure, or not part of an underlying disease. A problem or event is "unanticipated" when it was unforeseeable at the time of its occurrence. A problem or event is "unanticipated" when it occurs at an increased frequency or at an increased severity than expected, **AND**

- Related: A problem or event is "related" if it is possibly related to the research procedures.

Adverse Event Reporting Period

For this study, the study treatment follow-up period is defined from enrollment in the study to 6 months after balloon removal (12 months from balloon insertion). Adverse events will be captured and reported from enrollment to the end of the study treatment follow-up.

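### The Study Summary promises multivariable regression at p<0.05 to identify risk variables; Section 7 contains no such analysis, and 12 subjects cannot reliably support it

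*Combined protocol and SAP*

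**What the plan says.** The Statistical Methodology row of the Study Summary first calls the results mostly descriptive. It then adds: "Multiple linear and logistic regression analysis will be performed to determine significant variables relating to risk". The next sentence sets the criterion: "A p-value of < 0.05 will be considered statistically significant".

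Section 7 (Statistical Plan) opens: "This is a pilot study of 12 subjects only, so results will be largely descriptive". Apart from an unspecified reference to standard analysis, it names one method, t-tests or "alternative measures will be used to test whether weight loss was significant from baseline to each of the follow up points". It mentions no regression, no significance level, no risk outcome and no covariate.

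No other section says what risk means here (adverse events, failure to lose weight or metabolic risk), which variables enter the models, how many there are, or which test supplies the p-value.

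**The concern.** The two statements of the analysis plan do not match, and the sentence found only in the Summary makes the stronger claim: that the models will determine which variables matter, judged at a fixed threshold. Followed as written, it would sort covariates into significant and non-significant. With 12 subjects that sorting would depend heavily on the number and type of covariates, on the test the software reports and on chance separation in the data. Real predictors could be missed or false ones reported. Safety is part of the primary objective in Section 2 and the subjects are adolescents, so a reader could take either result as safety evidence.

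**Working it through.** The plan gives no power or precision figure for these models, so there is none to reproduce.

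**Inputs from the documents.** n = 12, single arm (Sections 5.2 and 7). Threshold 0.05 (Study Summary). Event rates from Section 1.4: "Pain and nausea are frequent side-effects after Orbera balloon implantation, occurring in up to 33.7% of subjects"; migration 1.4%; perforation 0.1%.

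**Assumptions, because the documents name none.** One to five covariates (k), independent of each other and, under the null, of the outcome. Covariates are either continuous or binary with prevalence 0.5. The 33.7% rate is an illustration only; 50% is added as the most favourable rate.

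**Step 1: expected events.**
- At 33.7%: 12 × 0.337 = 4.0 events.
- Migration: 12 × 0.014 = 0.17 events; P(none) = 0.986^12 = 0.844.
- Perforation: P(none) = 0.999^12 = 0.988.
- At an assumed 10% rate: P(none) = 0.9^12 = 0.282.

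With no events, no logistic model can be estimated.

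**Step 2: logistic regression under the null.** 4,000 simulated trials per setting, with separation checked by linear programming. Trials with 0 or 12 events, or a rank-deficient design, count as having no finite estimate; those with 0 or 12 events count as no rejection. Under separation the likelihood-ratio (LR) statistic uses the supremum of the likelihood. LR rows are for continuous covariates. The Monte Carlo standard error is below 1 percentage point.

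| | k=1 | 2 | 3 | 4 | 5 |
|---|---|---|---|---|---|
| No finite estimate, 33.7%, continuous | 2.2% | 7.3% | 18.1% | 35.1% | 59.1% |
| No finite estimate, 33.7%, binary | 22.2% | 41.7% | 60.2% | 73.7% | 85.5% |
| No finite estimate, 50%, continuous | 0.4% | 3.4% | 11.1% | 26.5% | 48.9% |
| No finite estimate, 50%, binary | 12.1% | 28.7% | 48.6% | 67.3% | 81.2% |
| LR false positive, one named coefficient, 33.7% | 8.9% | 12.1% | 16.9% | 21.1% | 24.8% |
| Same, among finite fits only, 33.7% | 7.7% | 7.7% | 7.0% | 6.8% | 6.4% |
| LR false positive, one named coefficient, 50% | 7.6% | 11.4% | 15.8% | 22.5% | 26.3% |
| LR false positive, any coefficient, 33.7% | 8.9% | 20.0% | 31.8% | 45.1% | 57.9% |

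The Wald test, applied where the estimate is finite, rejected a true null in at most 0.05% of trials.

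**Step 3: source of the LR excess at 33.7%.** The contribution of finite fits is P(finite) × (rate among finite fits − 0.05).
- k=1: 0.978 × (0.077 − 0.05) = 0.026, out of a total excess of 0.089 − 0.05 = 0.039. Most of it comes from finite fits.
- k=3: 0.819 × (0.070 − 0.05) = 0.016 out of 0.119. Most of it comes from fits with no finite estimate.
- k=5: 0.409 × (0.064 − 0.05) = 0.006 out of 0.198. The same holds, more strongly.

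**Step 4: logistic power.** For a true odds ratio of 4 per SD at 33.7% with k = 1, 3 and 5, Wald power is 0.25%, 0.03% and 0.00%. LR power is 49%, 54% and 47%, which cannot be taken at face value given the error rates in Step 2.

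**Step 5: linear regression.** 20,000 simulated trials per setting.
- Type I error for one prespecified coefficient is 4.8 to 5.3%, as it should be.
- At least one false p<0.05 for k = 1 to 5: 5.0, 9.2, 12.8, 14.9 and 16.8%. The independent-test formula gives 1 − 0.95^5 = 22.6% for five; the simulated figure is lower because tests in one model share a residual variance.
- Expected R-squared from noise is k/(n − 1) = k/11: 0.09 for one covariate, 0.27 for three, 0.45 for five.
- Power for a true correlation of 0.5 is 39% alone and 29% with three further noise covariates. Fisher-z check for the first: atanh(0.5) × √(12 − 3) = 0.549 × 3 = 1.65; 1 − Φ(1.96 − 1.65) ≈ 38%.
- True R-squared needed for 80% power on the overall F-test, with noncentrality 12R²/(1 − R²): 0.45 for one covariate, 0.60 for three, 0.72 for five.

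**The case against.** The strongest reply is that this is a declared pilot. The Summary, like Section 7, calls the results mostly descriptive, and it does so just before the regression sentence. Section 7 is silent on regression rather than opposed to it, and its reference to standard analysis could be stretched to cover it. With one or two continuous covariates separation is uncommon (0.4 to 7% in Step 2). The Summary does not exclude exact or penalised logistic methods, which would reduce the separation problem and move away from the choice between Wald and likelihood-ratio tests. A one-covariate linear model is valid.

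Much of this stands and limits the point. A reader might infer that regression cannot be fitted at all with 12 subjects, that logistic models will usually fail, or that the two sections flatly contradict each other. The documents do not support any of these. Linear models can be fitted, logistic failure depends on covariates that the plan never names, and Section 7 omits the analysis without ruling it out.

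Three things remain. The descriptive label does not cover a commitment to determine significant variables at 0.05, since nothing marks the regression as exploratory. Penalised or exact estimation handles non-finite estimates but does not supply the information that about four events in 12 subjects lack. And a general reference to standard analysis does not define an outcome, a covariate or a test.

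**Conclusion.** The point holds: the Summary commits to an analysis that the Statistical Plan does not contain and that 12 subjects cannot reliably support. At the illustrative 33.7% rate, ordinary logistic fitting fails in a small share of trials with one or two continuous covariates, and in a substantial share with binary covariates or with three or more continuous ones. The error depends on the test: Wald has almost no power, while likelihood-ratio tests exceed their nominal 5% even with one covariate. Linear models keep their nominal error for one prespecified coefficient but have low power, an inflated R-squared and growing false positives once several covariates are screened.

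The exact percentages rest on independent covariates, one to five of them, and on assumed event rates. At 50% the separation rates are lower but the conclusion is the same; for the rarer serious events it is worse.

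It would be a mistake to infer that the trial's main results or safety oversight are compromised. The Section 7 weight-loss tests, the stopping rules in Section 8.5 and the DSMB review in Section 8.6.1 do not use these models. The plan should be changed, but the defect does not undermine the trial.

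**What to change.** Delete the regression sentence from the Study Summary so that it agrees with Section 7. State that p<0.05 applies only to the prespecified within-subject change-from-baseline tests: weight in Section 7 and, if they are to be tested, the secondary endpoints in Section 3.3. Naming the secondary endpoints matters, because tying the threshold to weight alone would leave them with no criterion.

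If the investigators want to keep some modelling, move it to Section 7 and label it exploratory. Name the outcome and the covariate, use one covariate per model, report estimates with confidence intervals (exact or penalised for binary outcomes), and make no significance claim.

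The cost is one sentence deleted and one clause added, or a short paragraph in Section 7 if modelling is kept. No new data are needed. The downside is that no multivariable risk analysis will be reported.

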1.1 Background

The global rise in the prevalence of overweight and obesity among all ages and ethnic groups has become an epidemic that affects daily medical practices everywhere. The prevalence of pediatric obesity in the United States defined by a body mass index (BMI) measurement of $\geq 95\%$ or greater than 2 standard deviation (SD) age has increased from 4.2% 1965 to 17.6% now. This significant increase in pediatric obesity is becoming a major health problem in United States.[1-3] The contributory causes of this rapid increase are multifactorial including metabolic dysregulation, genes, environmental/socioeconomic stressors, and energy imbalance.[4] Pediatric obesity is known to be associated with increased morbidity and predisposes adolescents to become obese adult with long term complications. Obese children and adolescents are at increased risk for obstructive sleep apnea, metabolic syndrome, orthopedic disorders, hypertension, type 2 diabetes mellitus (DM2), and fatty infiltration into the liver that can range from nonalcoholic fatty liver disease (NAFLD) to nonalcoholic steatohepatitis (NASH) and cirrhosis. [5, 6] These comorbidities are also clearly associated with significant increase in outpatient visits, prescription drug use, and emergency room visits, resulting in decrease quality of life for these adolescents and significant increase medical care cost. [7] In view of the magnitude of the pediatric obesity problems, many centers are developing multidisciplinary approach programs to address childhood obesity and prevent its long-term complications. The current generalized approach usually includes changes in lifestyle, diet, and physical activity.[8] The challenge to this approach is that persistent lifestyle changes are difficult to achieve and long-term results are often disappointing.[9, 10] For all of these reasons, adolescents are increasingly undergoing surgical treatment for obesity, and systematic data collection in bariatric programs is needed to further shape adolescent bariatric surgery guidelines.[11] The paucity of long-term outcome and special ethical consideration created a major limitation to establishing unified indications and criteria for bariatric intervention in adolescents.[12] New research is underway with the intent to produce specific recommendations and guidelines for bariatric intervention in adolescents, based on numerous positive publications regarding the clinical impact of bariatric intervention on the early-onset obesity-related diseases.[13-16]

1.2 Investigational Device

The Orbera (Apollo Endosurgery, Austin, TX) is an elastic spherical balloon made of silicone, filled with 550 mL of saline solution, and is FDA approved for weight loss in adult US patients with body mass index between 30 to 40 kg/m². The deflated balloon comes preloaded on a catheter, which is blindly advanced trans-orally into the stomach. An endoscope is then advanced alongside it to ensure accurate placement of the balloon in the fundus. Under direct visualization, the balloon is then inflated by injecting saline solution through the external portion of the catheter. The Orbera balloon is currently used outside the United States including

a pilot trial for adolescent in the United Kingdom.[17] This intragastric balloon is typically implanted for 6 months and then retrieved endoscopically.

1.3 Preclinical Data

See PMA study of the Orbera intragastric balloon.

1.4 Clinical Data to Date

The Orbera™ Intragastic Balloon (Apollo Endosurgery, Austin, TX), previously known as the BioEnterics Intragastic Balloon (BIB) (Allergan, Irvine, CA) is an elastic spherical balloon made from silicone, filled with about 600 ml of saline and is placed in the stomach via upper endoscopy. This intragastric balloon (IGB) is designed to stay in place for 6 months prior to endoscopic removal and has been widely used in Europe, South America, and the Middle East with excellent safety profile. In an American Society of Gastroenterology and Endoscopy (ASGE) Bariatric Endoscopy Task Force systematic review and meta-analysis the pooled percentage of total body weight loss (TBWL) after the Orbera IGB implantation was 12.3% (95% CI, 7.91–16.73), 13.16% (95% CI, 12.37–13.95), and 11.27% (95% CI, 8.17–14.36) at 3, 6, and 12 months after implantation, respectively.[18] This was based on a review of 55 studies. This balloon is currently FDA approved for use in the United States after a US randomized multicenter pivotal trial demonstrated similar efficacy. There is paucity of data about the use of IGB in adolescents. Despite the preference for avoiding surgical and invasive intervention for managing morbid obesity in adolescents, high relapse rates of current approaches and minimal adverse events of IGB can justify this nonsurgical bariatric interventions.[19] A recent pilot study suggested that IGB was a feasible and safe intervention in obese adolescents resulting in weight loss and improvement in their metabolic syndrome. [17] Another important application to this intervention comes from the noticeable increase in the incidence NAFLD and NASH in adolescents is increasing, resulting in significant morbidity and long-term complications such as liver fibrosis and cirrhosis.[20] Neuman et al, suggested that bariatric procedures including noninvasive ones such as IGB intervention can resolve the liver involvement and prevent further complications.[21]

Another application comes from the growing evidence regarding the epidemiology of DM2 in adolescents and its multisystem health complications, but treatment options have lagged behind. Disease progression in adolescents occurs despite aggressive medical therapy and tends to be more aggressive than in adults with DM2. All of that evidence resulted in increased interest in the application of bariatric intervention for adolescents with DM2 and morbid obesity. This was the recommendation of recent review by Shah et al, who recommended bariatric intervention because of the evidence demonstrating improvement or remission in many adults with diabetes after bariatric intervention. [22]

The rates of adverse events after implantation of the Orbera balloon are pooled from a manual review of 68 studies (8500 implantations) and are summarized in Figure 1. Pain and nausea are frequent side-effects after Orbera balloon implantation, occurring in up to 33.7% of subjects. Medications such as proton pump inhibitors, antispasmodic drugs, and antiemetics are usually prescribed prophylactically before, during, and after balloon placement to prevent

or minimize these expected common side effects. Serious side-effects with Orbera balloon are rare with an incidence of migration and gastric perforation of 1.4% and 0.1%, respectively. Most of the reported perforations with the Orbera were in patients who had undergone previous gastric surgeries, which is a contraindication for use in the US.[18]

